2.5.5 Statistical model, hypothesis, and method of analysis

No hypotheses will be tested as per the protocol. All the analysis will have a descriptive purpose.

2.5.6 Handling of missing values/censoring/discontinuations for the safety endpoints

[figure not shown]
[figure not shown]
All available data, regardless of concomitant use of omalizumab, for the safety endpoints outlined in protocol [Section 9.4.1] will be reported. Missing data for these endpoints will not be imputed, except for the missing date as described in appendix 5.

2.6 Analysis of the secondary objectives

Secondary efficacy variables will be summarized by visit with descriptive statistics, which include absolute and relative frequencies for categorical variables and arithmetic mean, standard deviation, minimum, maximum, median and first and third quartile for continuous variables. Time to event variables will be summarized using Kaplan-Meier estimates. Time to event variables that are only analyzed during the treatment epoch will be cut-off at Week 52, otherwise all data available will be included in the analysis (no cut-off at Week 100).

Table 1-6 Secondary efficacy variables

Domain	Variable	Analyzed in treatment epoch	Analyzed in follow-up epoch
Clinical symptoms: total	Complete UAS7 response (UAS7 = 0)	Y	Y
	Achievement of UAS7 <= 6	Y	Y
	Change from Baseline in Urticaria Activity Score (UAS7)	Y	Y
	Time to achievement of complete UAS7 response for patients without response at extension study baseline	Y	N

Domain	Variable	Analyzed in treatment epoch	Analyzed in follow-up epoch
	Time to loss of complete UAS7 response for patients having achieved complete UAS7 response in E1 treatment period at Week 52	N	Y
			
	Time to UAS7 > 6 for patients having achieved UAS7 ≤ 6 in E1 treatment period at Week 52	N	Y
Clinical symptoms: hives	Complete hives response (HSS7 = 0)	Y	Y
	Change from Baseline in HSS7	Y	Y
	Time to achievement of complete hives response for patients without response at extension study baseline	Y	N
	Time to loss of complete hives response for patients having achieved complete hives response in E1 treatment period at Week 52	N	Y
Clinical symptoms: itch	Complete itch response (ISS7 = 0)	Y	Y
	Change from Baseline in Itch Severity Score (ISS7)	Y	Y
			

Note: Y: yes, N: no

2.6.1 Hives Severity Score (HSS7)

The number of hives will be recorded by the patient twice daily in their eDiary on a scale of 0 (none) to 3 (severe (greater than 12 hives)).

A weekly score (HSS7) will be derived by adding up the average daily scores of the 7 days. The weekly score will therefore range from 0 to 21. If one of the morning or evening scores is missing, then the non-missing score for that day (morning or evening) will be used as the daily score. Complete hives response is defined as $HSS7 = 0$.

Changes from baseline in HSS7 score will be computed and will be summarized along with the absolute values at each visit. Mean with 95% confidence interval will be displayed graphically over time to describe the score change during the study. In addition, HSS7 descriptive statistics will be summarized, [REDACTED].

For $HSS7=0$ response, summary tables and graphs by visit will display, the response rate with the 95% Clopper-Pearson exact confidence interval. In addition, $HSS7=0$ response will be summarized, [REDACTED].

Kaplan-Meier estimates of the time to first $HSS7=0$ response and of the time to first loss of response for patients having achieved response at Week 52, will be plotted and will be tabulated at defined time points.

For patients with concomitant use of omalizumab, HSS scores will be censored at the date of start of omalizumab and treated as missing onward.

2.6.2 Itch Severity Score (ISS7)

The severity of the itch will be recorded by the patient twice daily in their eDiary, on a scale of 0 (none) to 3 (intense/severe).

A weekly score (ISS7) will be derived by adding up the average daily scores of the 7 days preceding the visit. The weekly score will therefore range from 0 to 21. Partially missing diary entries will be handled in the same way as described for the hives severity score. Complete itch response is defined as $ISS7 = 0$.

Changes from baseline in ISS7 score will be computed and will be summarized along with the absolute values at each visit. Mean with 95% confidence interval will be displayed graphically over time to describe the score change during the study. In addition, ISS7 descriptive statistics will be summarized, [REDACTED].

$ISS7=0$ response will be summarized and plotted by visit and response rate with the 95% Clopper-Pearson exact confidence interval will be included in the analysis. In addition, $ISS7=0$ response will be summarized, [REDACTED].

For patients with concomitant use of omalizumab, ISS scores will be censored at the date of start of omalizumab and treated as missing onward.

2.6.3 The weekly Urticaria Activity Score (UAS7)

[figure not shown]
The UAS7 is the sum of the HSS7 score and the ISS7 score. The weekly UAS7 score will then range from 0 to 42. Complete UAS7 response is defined as $UAS7 = 0$.

[figure not shown]
Changes from baseline in UAS7 score will be computed and will be summarized along with the absolute values at each visit. Mean with 95% confidence interval will be displayed graphically over time to describe the score change during the study. In addition, UAS7 descriptive statistics will be summarized, [REDACTED].

[figure not shown]
UAS7=0 response will be summarized and plotted by visit and response rate with the 95% Clopper-Pearson exact confidence interval will be included in the analysis. In addition, achievement of UAS7 ≤ 6 will be summarized similarly. Also, UAS7=0 response will be summarized, [REDACTED].

Kaplan-Meier estimates of the time to first UAS7=0 response and of the time to first loss of response for patients having achieved response at Week 52, will be plotted and will be tabulated at defined time points. In addition, Kaplan-Meier estimates of the time to first UAS7 > 6 for patients having achieved UAS7 ≤ 6 at Week 52 [REDACTED], will be tabulated at defined time points.

For patients with concomitant use of omalizumab, UAS scores will be censored at the date of start of omalizumab and treated as missing onward.

2.6.10 Missing data handling and censoring process

There are 17 patients taking concomitant medication of omalizumab post treatment, which would have impact on the estimated efficacy during the post treatment period, especially for the patients stay in the follow-up period until the end of the study. In order to exclude the potential bias causing by the omalizumab use during post-treatment period, the efficacy data observed after start concomitant use of omalizumab will be set as missing.

Missing data handling of all weekly score coming from UPDD [REDACTED].

The weekly score (HSS7, ISS7, sleep/activity interference scores) will be derived by adding up the average daily scores of the 7 days preceding the visit. The weekly score will then range from 0 to 21. If one of the morning or evening score is missing, then the non-missing score for that day (morning or evening) will be used as the daily score.

For each weekly score from UPDD [REDACTED], except weekly total rescue medication, if one or more of the daily scores are missing, then the following principles will be applied to handle the missing data:

- If a patient has at least 4 non-missing daily scores within the 7 days prior to the study visit, then the weekly score will be calculated as the sum of the available eDiary scores of that week, divided by the number of non-missing days multiplied by 7.
- If there are less than 4 non-missing daily scores within the prior 7 days, then the weekly score will be missing for that week.

For rescue medication, if one or more of the daily number of tablets are missing, then the total weekly number of tablets will be missing.

The weekly Urticaria Activity Score is the sum of both the HSS7 score and the ISS7 score and will be missing if at least one of them is missing.

For all display of response rate by week, the rate will be obtained by dividing the number of responses by the total number of patients in the group analyzed, whatever if some of these patients analyzed have missing data on this week or not.

For the response rate analysis, for patients with missing data either due to discontinuation or due to insufficient eDiary data during that week or the start concomitant use of omalizumab, data imputation of the response will be done using the worst-case scenario (i.e. non-responder). For the patients completing the study, there will be no more imputation applied after the end of study visit. For the patients discontinuing the study early or start concomitant use of omalizumab, the imputation will be applied up to Week 100.

Duplicate data handling of questionnaires

For HSS7, ISS7 and UAS7, the daily score is derived from the average of morning and evening scores. All other questionnaires are completed either daily or at visits. If any of those questionnaires are completed more than once per day or visit (depending on the questionnaire schedule), then the worst outcome (i.e. the highest score) of the duplicate observations will be used in the analysis.

Censoring of time to response.

Time endpoints, such as time to first complete hives response, will be considered censored at the date of the last non-missing weekly score up to E1 Week 52, for any non-responder.

Censoring of time to loss of response.

For any patient maintaining response, the time to loss, such as time to first loss of complete hives response for patients who completed the treatment epoch and achieved complete hives response at Week 52, will be considered censored at the date of the last non-missing weekly score or at the date of start concomitant use of omalizumab.

Note that time to loss of response will be missing for all patients without having achieved the response in the E1 treatment period at study week 52.

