- No study treatment will be given during the post-treatment follow-up epoch; however, patients are allowed to take background medication and rescue medication. If a subject relapses i.e. develops symptoms with an UAS7 ≥ 12 , the investigator should be contacted for an ad-hoc visit to consider treatment with standard of care or other therapy.

Figure 3-1 Study design

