2.4.2 Prior and concomitant therapies

Prior and concomitant medication / surgery and medical procedures

Prior medications are defined as treatment taken and stopped prior to first dose of the core study drug. Prior medications were reported and analyzed in the core study and will not be reported in the extension study.

Listings will be provided for the medications and for the significant surgeries and medical procedures which were ongoing at the end of the core study or started after the end of the core study, and ended prior to first dose of the extension study drug.

Concomitant medications are defined as any medication given at least once after the first day of first extension study drug dose, and will be summarized on the safety set.

In case of missing end date the medication will be considered as concomitant. If it is partially missing, then the medication month and year will be compared to the month and year of the

first injection date, to know if the medication stopped prior to the drug or not. In case of uncertainty the medication will be considered as concomitant.

Medications will be identified using the Novartis Drug and Therapy Dictionary (NovDTD) including the Anatomical Therapeutic Chemical (ATC) code. Medications will be presented in alphabetical order, by ATC code.

Concomitant medications for CSU starting or continuing during the treatment epoch or during the follow-up epoch will be summarized for each epoch, by type of therapy, ATC code, preferred term and symptom treated. Non-urticaria related concomitant medications starting or continuing during the treatment epoch or during the follow-up epoch will be summarized for each epoch, by ATC code and preferred term.

Concomitant significant surgeries and medical procedures starting or continuing during the treatment epoch or during the follow-up epoch will be summarized for each epoch, by primary system organ class and MedDRA preferred term.

Concomitant use of rescue medication

Concomitant use of rescue medication (using eCRF information) starting during the treatment epoch or during the follow-up epoch will be summarized for each epoch, by ATC code and preferred term.

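### In follow-up, omalizumab is the only new therapy whose start removes efficacy scores, so by-week response rates and means handle other new CSU therapies under a different convention

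*SAP*

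**What the plan says.** **Omalizumab rule.** SAP 2.6.10 reports "There are 17 patients taking concomitant medication of omalizumab post treatment" and, to avoid bias in post-treatment efficacy, directs that "the efficacy data observed after start concomitant use of omalizumab will be set as missing". SAP 2.6.1 to 2.6.3 repeat this for HSS, ISS and UAS, and section 4 lists it as a change from the protocol.

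**Response rates.** Non-response is imputed for "missing data either due to discontinuation or due to insufficient eDiary data during that week or the start concomitant use of omalizumab". On the horizon: "For the patients discontinuing the study early or start concomitant use of omalizumab, the imputation will be applied up to Week 100". On the denominator: "the rate will be obtained by dividing the number of responses by the total number of patients in the group analyzed".

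**Time to loss of response.** A patient still in response "will be considered censored at the date of the last non-missing weekly score or at the date of start concomitant use of omalizumab".

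**Therapy after relapse.** Under Protocol 3.1, when UAS7 reaches 12 or more in follow-up, "the investigator should be contacted for an ad-hoc visit to consider treatment with standard of care or other therapy". Protocol 5.6.1 makes leaving the study after relapse optional.

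**Prohibited therapy.** Protocol 5.5.8 and Table 5-1 bar listed treatments once study treatment has started, among them routine systemic corticosteroids, cyclosporine A, methotrexate and intravenous immunoglobulin. A patient who used one must stop it to stay in the study.

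**Other CSU therapy.** SAP 2.4.2 plans a descriptive summary: "Concomitant medications for CSU starting or continuing during the treatment epoch or during the follow-up epoch will be summarized for each epoch". No readable text attaches an efficacy rule to it.

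**The concern.** The SAP's reason for the omalizumab rule is that active treatment started after QGE031 ends distorts the post-treatment results. That reason does not depend on the drug. Yet a patient who relapses, starts a different new CSU therapy and remains in the study can count again as a by-week responder and pull the follow-up mean UAS7 down.

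At stake is the meaning of the follow-up figures. Protocol 3.2 gives the 48 weeks after treatment the task of evaluating, among other things, sustained remission. A weekly rate that scores omalizumab starters as failures and other starters as observed measures neither benefit off treatment nor outcome regardless of later therapy.

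**Working it through.** **Step 1. Follow three relapsers through the rules.** Each reaches UAS7 ≥ 12 in follow-up.

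| Patient | By-week response rates | Follow-up means | Time to loss of UAS7=0, or to UAS7>6 |
|---|---|---|---|
| Leaves the study | Non-responder to Week 100 | No further scores | Already lost at relapse |
| Stays, starts omalizumab | Non-responder to Week 100 | Set to missing | Already lost at relapse |
| Stays, starts another new CSU therapy | Observed score | Observed score | Already lost at relapse |

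Only the third patient can be credited with response on a replacement therapy, and only in the two middle columns.

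**Step 2. Check the first-loss endpoints.** UAS7 ≥ 12 is above both 0 and 6, so complete UAS7 response and UAS7 ≤ 6 are lost before any therapy given for relapse. For hives the protection is slightly weaker. ISS7 alone can reach 21, so a patient relapsing on itch only could still have HSS7=0. Otherwise these endpoints are exposed only if new therapy begins before loss.

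**Step 3. Check sustained remission.** Protocol 2.2 and SAP 1.2.2 define it as keeping UAS7 ≤ 6 throughout follow-up among patients in remission at end of treatment. A relapse ends that status for good. SAP Table 1-4 (Japanese subgroup) instead glosses it as achieving UAS7 ≤ 6. If it is analysed as by-visit achievement, it is exposed like the weekly rates.

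**Step 4. Check whether Table 5-1 closes the route.** It bars the main routine alternatives but not every therapy: for corticosteroids and the listed immunosuppressants, routine means daily or every other day for 5 or more consecutive days. Someone who used a barred drug and stopped may continue. SAP 2.2.1 has a deviation category for prohibited medication, but no deviation excludes anyone from the analysis set, and no readable rule removes scores recorded during such use.

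**Step 5. Size.** The plan states no figure that depends on this rule, so there is nothing to reproduce. Inputs:
- N = 240, the approximate enrolment expected in Protocol 9.7
- 17 omalizumab users (SAP 2.6.10)
- n, the number starting another new therapy, and r, the share of them counted as responders in a given week; both are assumed

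Formula: shift in a weekly rate = n × r / N.

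- One responder: 1/240 = 0.42 points.
- Yardstick: 17/240 = 7.1% (8.5% of 200, 5.7% of 300). At N = 240 this is the most the omalizumab rule itself can move a weekly rate.

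| n (assumed) | r = 0.5 | r = 0.8 | r = 1 |
|---|---|---|---|
| 5 | 1.0 | 1.7 | 2.1 |
| 10 | 2.1 | 3.3 | 4.2 |
| 17 | 3.5 | 5.7 | 7.1 |

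Shifts are in percentage points. For scale, an assumed rate of 72/240 = 30.0% has a Clopper-Pearson 95% interval of 24.3 to 36.2. Adding 10 credited responders gives 82/240 = 34.2% (28.2 to 40.5); adding 17 gives 89/240 = 37.1% (31.0 to 43.5).

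**The case against.** The strongest reply is that singling out omalizumab is largely coherent. Protocol 1.1 and 3.6 name the alternatives after antihistamines: omalizumab, cyclosporine A or other immunosuppressants, montelukast, and repeated oral glucocorticoids. Omalizumab has its rule, montelukast is background medication, and routine cyclosporine A and corticosteroids are in Table 5-1. What remains is short or non-routine courses, unlisted drugs and deviations. This narrows the gap, possibly to few patients, but does not close it, because Protocol 3.1 and 5.5.8 are not reconciled for follow-up.

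Other replies that stand in part:
- The study is single-arm and descriptive with safety as its primary objective, so no test is affected.
- The patient counts are assumptions, and the true effect could be zero. Omalizumab is a generous yardstick because SAP 2.4.2 describes it as allowed.
- Copying the permanent omalizumab rule to a course of a few days would impose non-response for the rest of follow-up, which is hard to defend.
- Setting relapsers to missing in the means is itself informative and can leave those means looking favourable.

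A reader might also infer more than the documents support. Omalizumab is not the only trigger of non-response, since discontinuation and insufficient diary data count too. Protocol 3.1 cannot be read as opening every therapy while Table 5-1 stands. Nor are the duration-of-response curves inflated by therapy given after relapse, apart from the hives exception in Step 2.

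**Conclusion.** The point holds for the by-week follow-up rates (UAS7=0, UAS7≤6, HSS7=0, ISS7=0) and for the follow-up means. Both mix two conventions, and where they are in error the likely direction is to overstate benefit off treatment. Sustained remission is exposed only if it is analysed as the Table 1-4 label suggests.

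The size is not known. It rests on an assumed N of about 240 and an unreported number of patients on other new therapies. Parts of SAP 2.6 and section 4 are redacted, so a wider rule there cannot be fully excluded; every readable statement of the rule names omalizumab alone.

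**What to change.** 1. In SAP 2.6.10, at least as a prespecified sensitivity analysis, treat the start in follow-up of any new systemic CSU therapy beyond background and rescue H1-AH, H2-AH and LTRA like omalizumab for response rates: non-responder up to Week 100. For short courses, state a limited window in advance.
2. Identify these starts from the CSU concomitant-medication data by a review completed before database lock. Include Table 5-1 drugs recorded as deviations.
3. Beside the follow-up means, report how many patients started omalizumab and how many another new therapy, and say how each group's scores were handled.
4. Align the sustained-remission label in SAP Table 1-4 with the definition in SAP 1.2.2.
5. Reconcile Protocol 3.1 with 5.5.8 and Table 5-1 on which therapies may be used in follow-up. Which they are is for the sponsor to decide.

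The cost is SAP wording, one extra set of response tables and a medication review. The medication data are already collected, so no new collection should be needed. The downside is more imputed non-response and slightly lower follow-up rates.

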5.6 Study completion and discontinuation

5.6.1 Study completion and post study treatment

Study completion for individual patients will be when he/she has completed the extension study 52 weeks of treatment and the full follow-up epoch up to and including Visit 405.

Treatment completion will be when the patient completed the full 52-week treatment epoch. If patients relapse during the follow-up epoch of the extension study as defined by a UAS7 \geq 12, they will be allowed to exit the study if desired and receive conventional therapy at the discretion of the investigator.

Completion of the study will be considered when all patients will have completed 52 weeks of treatment epoch and the full follow up epoch or have prematurely withdrawn from the study.

Information on the subject's completion or discontinuation of the study and the reason for discontinuation of the study will be recorded on the appropriate Study Epoch Completion eCRF page.

When the patient has completed all scheduled study assessments, the investigator must call or logon to the IRT system to record the patient completion as per above completion definitions.

The following is recommended for initiating other treatment outside or post study:

- A wash-out of QGE031 of at least 4 months is advised prior to commencing Xolair® treatment

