2.1.1 Assessment windows

No assessment windows are defined for this study. Consequently, all by-visit summaries will be performed as per below scheduled visits.

Table 1-1 Assessment windows for scheduled visits

Analysis Visit	E1 Week	E1 Scheduled Day	Visit Window
E1 Baseline	Baseline	-21/-14, 1	Up to Day 1
E1 Week 4	4	29	NA
E1 Week 8	8	57	NA
E1 Week 12	12	85	NA
E1 Week 16	16	113	NA
E1 Week 20	20	141	NA

E1 Week 24	24	169	NA
E1 Week 28	28	197	NA
E1 Week 32	32	225	NA
E1 Week 36	36	253	NA
E1 Week 40	40	281	NA
E1 Week 44	44	309	NA
E1 Week 48	48	337	NA
E1 Week 52	52	365	NA
E1 Week 64	64	449	NA
E1 Week 76	76	533	NA
E1 Week 88	88	617	NA
E1 Week 100	100	701	NA

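### A calendar-defined diary Week 100, combined with the all-patient denominator, counts completers whose final visit is about five or more days early as Week 100 non-responders

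*SAP*

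**What the plan says.** Five provisions bear on the Week 100 response rate.

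- **Diary week.** SAP 2.1.3 (Table 1-2) defines week w by study day, from 7(w-1)+1 to 7w, counted from the first extension dose.
- **Score derivation.** SAP 2.6.10 instead sums the daily scores over the seven days before the visit and requires at least four non-missing days in that span. SAP 2.6.2 uses the same visit anchor for itch, and protocol 6.4.1.1.1 and 6.4.1.1.2 use it for hives and itch.
- **Denominator.** For response rates by week, SAP 2.6.10 divides by "the total number of patients in the group analyzed, whatever if some of these patients analyzed have missing data on this week".
- **Imputation.** SAP 2.6.10 sets a missing response to non-response. It then separates two groups: "For the patients discontinuing the study early or start concomitant use of omalizumab, the imputation will be applied up to Week 100", but "For the patients completing the study, there will be no more imputation applied after the end of study visit".
- **Visit timing.** Visit 405 is scheduled for Day 701 (SAP Table 1-1, protocol Table 6-1). SAP 2.1.1 states: "No assessment windows are defined for this study". Under protocol 5.6.1, a patient completes the study after the 52 treatment weeks and the "full follow-up epoch up to and including Visit 405".

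**The concern.** The same weekly score has two anchors, and the SAP does not say which one governs a completer whose last visit is early. Under the calendar anchor that patient can lose the Week 100 score purely because of the appointment date. The fixed denominator then turns the missing score into a non-response.

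The sentence exempting completers from further imputation reads as if it protected them. It could do so only if those patients also left the denominator, which the denominator rule rules out. Two programmers could therefore report different Week 100 rates from the same data.

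Week 100 is the 48-week post-treatment landmark. The secondary objective is sustained remission over those 48 weeks, and SAP Table 1-4 labels achievement of UAS7<=6 as sustained remission for the Japanese subgroup, where a few early visits would weigh more. The exact confidence intervals in SAP 2.6.1 to 2.6.3 would be computed around the shifted rate.

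**Working it through.** **Step 1: reproduce the plan's calendar.** From Table 1-2, Week 100 runs from 7 x 99 + 1 = Day 694 to 7 x 100 = Day 700. The scheduled visit is 7 x 100 + 1 = Day 701, which matches Table 1-1. On schedule, the whole diary week precedes the visit.

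**Step 2: count Week 100 diary days by the day of Visit 405.** This assumes that diary entry stops at the final visit and that no earlier day is missing.

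| Visit 405 on Day | Days early | Diary days before the visit | Including an entry on the visit day |
|---|---|---|---|
| 701 or later | 0 | 7 | 7 |
| 698 | 3 | 4 | 5 |
| 697 | 4 | 3 | 4 |
| 696 | 5 | 2 | 3 |
| 695 | 6 | 1 | 2 |
| 694 | 7 | 0 | 1 |

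At least four days are needed. On or before Day 696 the calendar Week 100 score is missing on either count. Day 697 depends on whether the morning entry on the visit day is used. Under the visit anchor, the last seven diary days always precede Visit 405, so an early date alone never loses the score.

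**Step 3: test the imputation sentence.** Take N = 240 (expected enrolment, protocol 9.7) and assume 192 completers, of whom 50% respond, with 10 seen too early. Non-completers count as non-responders, as planned.

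- All Week 100 scores available: 0.5 x 192 / 240 = 96/240 = 40.0%.
- Early completers not imputed, denominator fixed: 0.5 x 182 / 240 = 91/240 = 37.9%.
- Early completers imputed as non-responders: (91 + 0)/240 = 37.9%.
- Early completers removed from the denominator: 91/230 = 39.6%.

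The second and third results are identical. The loss therefore comes from the calendar week and the fixed denominator together, not from the decision to stop imputing.

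**Step 4: size.** With E early completers whose response rate is p, the change in the reported rate is -(p x E)/N. Ranges below use N = 240, 20-40% of patients not completing (192 or 144 completers) and p of 30-50%. Everything except N is assumed.

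| Completers seen too early | Smallest loss | Largest loss |
|---|---|---|
| None | 0 | 0 |
| about 5% | 0.3 x 7/240 = 0.9 points | 0.5 x 10/240 = 2.1 points |
| about 10% | 0.3 x 14/240 = 1.75 points | 0.5 x 19/240 = 4.0 points |
| about 20% | 0.3 x 29/240 = 3.6 points | 0.5 x 38/240 = 7.9 points |

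The change can never be positive, because a lost score can only remove a responder from the numerator.

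**Step 5: analyses outside this rule.** Under SAP 2.6.10, time to loss of response for a patient still in response is censored at the last non-missing weekly score or at the start of omalizumab. It does not use the all-patient denominator.

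**The case against.** The strongest reply is that the SAP already contains the remedy. SAP 2.6.10 anchors the score to the visit, SAP 2.1.1 summarises by scheduled visit, and SAP 2.6.3 presents response rates by visit. On that reading no completer with adequate diary data loses Week 100. This is correct if the visit anchor governs. However, SAP 2.1.3 defines the weeks for these same diary scores by study day, and the denominator rule is written for displays by week. The text does not choose between them.

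A second reply is that early final visits may be rare. Protocol section 6 asks for visits on the designated day or near it, and SAP 2.1.1 concerns analysis windows, not scheduling. That stands: a visit must be about five days early before a score is lost, and the documents give no count. SAP section 4 acknowledges only that visit dates may not fall exactly on schedule, in the setting of last dose plus four weeks.

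A third reply is that these are descriptive secondary rates in a safety study with no hypothesis tests (SAP 2.5.5). That also stands and limits the importance of the point.

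A reader might infer from the completer sentence that the lack of imputation itself depresses the Week 100 rate. Step 3 shows that it does not. A reader might also see bias in holding early discontinuers and omalizumab starters as non-responders to Week 100. That is a stated worst-case convention for other patients, not an error.

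**Conclusion.** The concern holds as a conflict between two definitions of the weekly score. Under the calendar definition and the fixed denominator, it misclassifies in one direction only. It affects completers with Visit 405 on or before Day 696 (and Day 697 if the visit-day entry is not used). It reaches only the Week 100 rates for UAS7=0, UAS7<=6, HSS7=0 and ISS7=0.

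The effect is zero when final visits are on schedule. About 1 to 8 points for 5-20% early completers is an illustration resting on the assumed completion and response rates in Step 4 and on early completers responding like the others. It is not an estimate for this trial, and the documents do not support a claim that the reported rates are materially too low. The completer sentence does no harm under the fixed denominator, but it has no function there either and should be reconciled with it.

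**What to change.** In SAP 2.6.10, state that for patients who complete the study the Week 100 score uses the last seven diary days before Visit 405, under the same four-of-seven rule. State also that response-rate displays end at Week 100 for everyone. Table 1-2 has no last week, and the absence of a Week 100 cut-off in SAP 2.6 concerns time-to-event variables only. With both statements in place, the sentence on stopping imputation for completers can be deleted or reworded to agree with the denominator rule. Non-responder imputation for early discontinuers and omalizumab starters stays as planned.

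The cost is SAP wording and one derivation, with no new data. The downside is that for a few completers the Week 100 score lies some days off its nominal time.
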